5.2 Research Procedures

5.2.1 Outcomes.

Cognition: This study will involve several neuropsychological tests of cognitive functioning. Based on our pilot work, the primary neuropsychological outcome for measuring cognitive processing speed (CPS) in the current proposal will be the oral version of the Symbol Digit Modalities Test (SDMT) [35]. This test is considered a more pure measure of CPS, as it relies less on working memory (i.e., the central executive) than other neuropsychological measures that are commonly used in MS research (i.e., the Paced Auditory Serial Addition Test; PASAT) [36]. The SDMT further is a better predictor of whole-brain atrophy and T2-lesion volume than the PASAT [36]. Indeed, the SDMT has emerged as the best predictor of future cognitive decline in persons with relapsing-remitting MS [37]. As such, it is often considered to be a proxy of generalized cognitive

impairment in this population [38]. The current proposal further will include other exploratory neuropsychological measures of CPS. Those measures include the PASAT [39], modified flanker task [40], Pattern Comparison Test [41], and DKEFS Trail-Making and Color-Word Interference Tests [42]. Such measures will be included to examine the generalizability of the effects of treadmill walking exercise training on the overall construct of CPS. Those tests have strong psychometric properties (e.g., [43]), and are commonly-used to document the efficacy of cognitive rehabilitation interventions in persons with MS (e.g., [44]).

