5.2.2 Protocol Overview. The proposed study involves a single-blind, randomized controlled trial (RCT) design. Participants will undertake baseline assessments, and will then be randomly assigned into either the 3-month intervention or 3-month active control condition. Following the 3-month study period, participants will return to the laboratory and complete follow-up outcome measures (i.e., the same measures as baseline, using alternate forms where applicable) by assessors who are unaware of which condition participants were randomly assigned to.

5.2.3 Baseline Testing. The baseline outcome assessments will be spread out across 2 visits for minimizing fatigue and interference from cognitive tests. There will be approximately 2 days separating each of these testing visits. Collectively, baseline testing will involve completion of the in-person screening measures, neuropsychological tests, measures of walking, physical function tests, questionnaires, cardiorespiratory fitness test, and MRI scan. Importantly, all data collection will be done in-person, and will not involve collection of data from medical records.

5.2.3.1 Baseline Visit 1: In-Person Screening Session. Once the project coordinator receives the verification of the participant's definite MS diagnosis and confirmation of being on at least 6-months of a stable DMT regimen, the project coordinator will schedule the participant for the first baseline testing visit via telephone—this will also include several in-person screening measures that will take place at the outset of this session. Baseline Visit 1 (i.e., including the in-person screening component) will occur at Kessler Foundation. Participants will complete the following procedures during the in-person screening session within the first baseline testing visit:

- Participants will first provide written informed consent
- Participants will then undertake the MMSE
 - In order to participate in the remainder of the study, participants will demonstrate scores of 21 or higher
- Participants will then undertake the SDMT
 - The SDMT involves pairing 9 abstract geometric symbols with single-digit numbers as quickly and accurately as possible over 90 seconds
 - In order to participate in the remainder of the study, participants will demonstrate slowed CPS based on SDMT scores at least 1 SD below the regression-based normative score for healthy controls (i.e., 16th percentile)

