- DKEFS Color-Word Interference Test: Participants read words of colors that are written in a certain color ink, and then participants are instructed to name the color ink that the word is written in, as quickly and accurately as possible
- Spatial perception test:
 - Judgement of Line Orientation Test: Participants are shown two different lines and are asked to tell the examiner whether the angles of the two lines are the same
- Executive functioning test:
 - DKEFS Sorting Test: Participants are asked to sort 6 different cards in as many ways as possible in a 4-minute period
- IQ Test:
 - Weschler Test of Adult Reading: Participants are asked to pronounce a series of words correctly
- 6MW Test:
 - Participants are asked to walk as fast and as far as possible for 6 minutes
 - During the 6MW test, a researcher will be within an arm's reach at all times
- T25FW Test:
 - Participants walk as quickly and as safely as possible over a 25-foot distance; 2 trials are performed. During the T25FW, a researcher will be within an arm's reach at all times
- Sit and Reach Test:
 - Participants will be seated on a mat, with their legs extended. Participants will be asked to bend at the waist and try to touch their toes (reaching as far as possible without bending the knees).
- Graded exercise test to exhaustion:
 - This will be performed on a motor-driven treadmill and an open-circuit spirometry system, using a modified Balke protocol (see above for the full procedure).

5.2.3.3 Baseline Visit 2. 2-days following the completion of Baseline Visit 1, participants will complete Baseline Visit 2, which will take place at the Rocco Ortenzio Neuroimaging Center at Kessler. During Baseline Visit 2, participants will complete the following procedures, as described above:

- Cognitive Tests:
 - Learning and memory tests:
 - California Verbal Learning Test-II: Participants are read a list of 16 words and are instructed to remember as many words as possible, and repeat the list back to the examiner
 - Brief Visuospatial Memory Test-Revised: Participants are shown a page with 6 abstract geometric figures, and then after a 10 second study period, are asked to draw the figures on a blank sheet of paper from memory
 - Verbal fluency test:
 - Controlled Oral Word Association Test: Participants are asked to name as many words beginning with the letters F, A, and S as possible in a 60 second period
- Questionnaires: EXSE, FAMS, PASR-12, NEO-FFI, BDI, HADS (These items are attached)

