The primary analysis will involve a statistically efficient, hierarchical step-down testing approach using ANCOVA models to examine differences in post-test outcomes of CPS and thalamocortical RSFC (i.e., examining group differences in follow-up outcomes, adjusting for baseline as covariate). The hierarchical step-down approach presents a series of conditional hypothesis tests after the primary hypothesis is assessed. This *a priori* specifies the importance and order of the testing so that each hypothesis is tested in order, until the first non-significant result occurs. Once a null-hypothesis is not rejected, all formal testing will stop, and all subsequent results will be reported as *post-hoc* and/or descriptive. This protects against Type I error as it assumes that the outcomes are correlated, and the overall *p*-value is protected by reporting the largest *p*-value for all the tests. As the primary study outcome involves CPS based on SDMT scores, we will first perform an ANCOVA model on follow-up SDMT score, with group (intervention or control) as a between-subjects factor and baseline SDMT score as the covariate. If statistically significant (i.e., *p*<.05), we will then assess the effects of the intervention on the general construct of CPS using MANCOVA and on the individual CPS tests using separate, univariate ANCOVA models.

Regarding thalamocortical RSFC, the next set of analyses will involve performing ANCOVA models on follow-up RSFC between the thalamus and frontal cortical areas (e.g., SFG, MFG [21]), respectively, with group (intervention or control) as a between-subjects factor and baseline RSFC between the thalamus and frontal cortical areas, as the covariates. We will require an alpha of .05 (corrected for multiple comparisons) for significance for thalamocortical RSFC outcomes. The correction for multiple comparisons will be achieved by establishing a suitable voxel cluster-level threshold through Monte Carlo simulations (using the 3dClustSim program, part of the AFNI suite of image analysis programs). Based on our pilot work [19,21], we expect significant group differences in SDMT score and RSFC between the thalamus and frontal cortical areas, respectively, at follow-up after controlling for baseline scores, whereby participants who are randomly assigned to the intervention group will demonstrate greater SDMT scores and stronger thalamocortical RSFC at follow-up compared with those who are randomly assigned to the control group.

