Statistical Analysis. The data analyses will be overseen by [name] and follow intent-to-treat principles (i.e., include all persons regardless of dropout). In the case of a drop-out, missing data will be imputed by carrying the last observed value forward. We further will perform exploratory data analyses only in those who completed follow-up testing (i.e., completer's or per protocol analysis) and in those who demonstrated good adherence (i.e., attended at least 83% of sessions) and compliance. The analytic plan will account for several potential confounders of the effects of progressive TMWX training on the outcome measures. These include MS duration, BMI, age, sex, cognitive reserve, T2-lesion volume, and relapse rate. If these variables differ between groups, they will be included as additional covariates in the following analyses.

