Specific Aim 1. The primary analysis will involve a statistically efficient step-down testing approach using ANCOVA models to examine changes in CPS and thalamocortical RSFC (i.e., examining group differences in follow-up outcomes, adjusting for baseline). As the primary study outcome involves CPS based on SDMT scores, we will first perform an ANCOVA model on follow-up SDMT score, with group (exercise or control) as a between-subjects factor and baseline SDMT score as the covariate. If statistically significant (i.e., $p<.05$), we will then assess the effects of the intervention on thalamocortical RSFC. This second step will involve performing two separate ANCOVA models on follow-up RSFC between the thalamus and right MFG and ACC, respectively, with group (exercise or control) as a between-subjects factor and baseline RSFC between the thalamus and right MFG and ACC, respectively, as the covariates. We will require an alpha of .05 (corrected for multiple comparisons) for significance for thalamocortical RSFC outcomes. The correction for multiple comparisons will be achieved by establishing a suitable voxel cluster-level threshold through Monte Carlo simulations (using the 3dClustSim program, part of the AFNI suite of image analysis programs). Based on our pilot work¹², we expect significant group differences in SDMT score and RSFC between the thalamus and right MFG and ACC, respectively, at follow-up after controlling for baseline scores, whereby participants who are randomly assigned to the exercise group will demonstrate greater SDMT scores and stronger thalamocortical RSFC at follow-up compared with those who are randomly assigned to the control group.

Specific Aim 2. We will examine RSFC between thalamus/right MFG, and RSFC between thalamus/ACC, respectively, as two potential mediators of the effects of TMWX training on CPS, consistent with the methodologies of Baron and Kenny⁸⁹ and MacKinnon et al⁹⁰. This statistical mediation approach is consistent with the proposed gold standard approach for examining exercise-related mechanisms of cognitive

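### The primary SDMT ANCOVA always adjusts for one score only, the eligibility SDMT; adding the other processing-speed tests already taken at Baseline Visit 1 would gain some precision at almost no cost

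*Combined protocol and SAP*

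**What the plan says.** **When the SDMT is given.** Under protocol 5.2.3.1, "Participants will then undertake the SDMT", and to continue "participants will demonstrate slowed CPS based on SDMT scores at least 1 SD below the regression-based normative score for healthy controls". The test takes 90 seconds. It is not in the rest of Visit 1 (5.2.3.2). It is not in Visit 2 (5.2.3.3) either, where the cognitive tests are the CVLT-II, BVMT-R and COWAT. The second visit already exists: "2-days following the completion of Baseline Visit 1, participants will complete Baseline Visit 2".

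**The primary model.** Protocol 5.3 specifies follow-up SDMT with "group (intervention or control) as a between-subjects factor and baseline SDMT score as the covariate". The SAP, Specific Aim 1, specifies the same model, with "group (exercise or control) as a between-subjects factor and baseline SDMT score as the covariate".

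**Other covariates.** The SAP's Statistical Analysis paragraph lists MS duration, BMI, age, sex, cognitive reserve, T2-lesion volume and relapse rate, and adds "If these variables differ between groups, they will be included as additional covariates in the following analyses". Protocol 5.3 has the same condition and a similar list, without cognitive reserve.

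**Other CPS tests.** Protocol 5.2.1 names five further measures: the PASAT, a modified flanker task, Pattern Comparison, and the DKEFS Trail-Making and Color-Word Interference tests. Section 5.2.3.2 places them all at Visit 1. Their stated role is as exploratory outcomes, and none enters the SDMT model.

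**The concern.** A single 90-second score contains measurement error, and what it fails to capture about a participant's true speed stays in the ANCOVA residual. Five related measurements from the same day could recover part of that, but the SDMT model does not use them. The conditional covariates are no substitute, because they enter on the strength of group imbalance and not because they predict the outcome.

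Precision matters more than usual here for two reasons. The planned effect comes from a pilot against a waitlist in people without CPS impairment (SAP, Sample Size Considerations), whereas this trial uses an active control in people with impairment, so planned power of 0.80 leaves little room. Also, SDMT is the first step of the hierarchy in 5.3: if it is not significant, formal testing stops, including for thalamocortical connectivity.

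**Working it through.** **1. The plan's own figure.** Inputs from protocol 5.1.1 and the SAP: partial eta-squared 0.11, alpha 0.05, power 0.80, two groups, one covariate.
- f² = 0.11/0.89 = 0.1236.
- Noncentral F with noncentrality f² × N on 1 and N − 3 degrees of freedom gives N = 66, power 0.803.
- 66/0.75 = 88.

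Both stated figures reproduce.

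**2. Adding a composite of the other CPS tests (completers).** The documents give no correlations, so these are assumptions:
- r = correlation of baseline with follow-up SDMT, 0.7 to 0.9;
- c = correlation of the composite with SDMT, 0.5 to 0.7, taken as equal at baseline and follow-up.

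The proportional fall in residual variance is the squared partial correlation of composite with follow-up SDMT given baseline SDMT:

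v = c²(1 − r) / [(1 + r)(1 − c²)].

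Example, r = 0.8 and c = 0.6: 0.36 × 0.2 / (1.8 × 0.64) = 0.072/1.152 = 6.25%.

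Power uses f²/(1 − v), N = 66 and one further degree of freedom.

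| r | c | v | power |
|---|---|---|---|
| 0.7 | 0.5 | 5.9% | 0.83 |
| 0.7 | 0.7 | 17.0% | 0.87 |
| 0.8 | 0.6 | 6.25% | 0.83 |
| 0.9 | 0.5 | 1.8% | 0.81 |
| 0.9 | 0.7 | 5.1% | 0.82 |

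The power figures also assume that the pilot's 0.11 came from a model adjusting for one baseline SDMT. Selection at the eligibility cut-off left v essentially unchanged in simulation, as expected, because v is already conditional on the SDMT score used for selection.

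**3. The same under the planned LOCF.** The primary analysis carries the last value forward, so a dropout's follow-up SDMT is the baseline SDMT. Simulation with selection at the cut-off and 25% of values carried forward reduces the gain to about 1% (r = 0.9, c = 0.5) to 12% (r = 0.7, c = 0.7).

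**4. Repeating the SDMT at Baseline Visit 2.** Let ρ be the correlation of two SDMTs two days apart, also not in the documents. If everyone completes and everyone has both scores, using their mean as covariate lowers residual variance by

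r²(1 − ρ) / [(1 + ρ)(1 − r²)].

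Example, r = 0.8 and ρ = 0.9: 0.64 × 0.1 / (1.9 × 0.36) = 9.4%. With r from 0.7 to 0.9, and ρ equal to r or up to 0.10 higher (capped at 0.97), the range is about 7% to 22%.

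Those conditions do not fit this trial. The first institution's share is 88 − 72 = 16 by the SAP or 88 − 65 = 23 by protocol 5.1.1, and those participants would lack the repeat. Simulation with selection, 25% LOCF and 23 of 88 without the repeat (single score plus an indicator for them) gives about 4% to 11%, and about 3% in the corner r = 0.9, ρ = 0.97. Put through the step 2 power formula as a rough guide, 4% to 11% corresponds to 0.82 to 0.85.

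**The case against.** **Nothing is wrong with the plan.** ANCOVA on a single baseline is standard and valid, and the sample size meets its stated target. This stands, and it limits the point to an improvement.

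**A reader might infer that using the eligibility score as covariate biases the result through regression to the mean.** The documents do not support that. Participants are randomised after the score is taken, so regression to the mean is expected equally in both arms.

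**A reader might also infer that a repeat SDMT would cut residual variance by 7% to 22%.** That range rests on correlations the documents do not give, and on everyone completing with two scores. Its top end needs scores 12 weeks apart to correlate as highly as scores two days apart. Over a wider range of correlations (r from 0.5, ρ up to 0.95) the gain falls to about 1%.

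**The repeat has side effects.** Section 5.2.7 makes the follow-up visits identical to baseline, so a second follow-up SDMT would appear and it would be unclear which is primary. It would also be unclear which baseline value LOCF carries forward. Section 5.2.1 calls for alternate forms at each session without saying how many SDMT forms exist, and 5.2.3 splits the visits partly to limit fatigue and interference between tests. All of this stands, and is why the repeat is optional here.

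**The composite's benefit is also assumed, and its construction must be defined.** True. Its low end is negligible, but it uses data already scheduled for collection.

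**Conclusion.** The point holds as a precision improvement. The SDMT model has one unconditional covariate, a single score that also sets eligibility, and leaves related Visit 1 data unused. Adding the composite would lower residual variance by about 2% to 17% in completers, or about 1% to 12% with 25% LOCF, under the correlations assumed above. A repeat SDMT would add about 4% to 11% over the single-score model once LOCF and the participants without a repeat are allowed for. The two gains were computed separately and should not be summed. Neither the validity of the comparison nor the stated sample size is in question.

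**What to change.** **Main change (SAP wording only).** Before unblinding, specify that the SDMT ANCOVA includes, whether or not groups differ, both baseline SDMT and a baseline composite of the other Visit 1 CPS tests. One workable definition is the mean of z-scores standardised on the pooled baseline sample, signed so that higher means faster. Name the score taken from each test and the rule for a missing component, and confirm that participants from the first institution have the same tests. The cost is one degree of freedom and a paragraph of text.

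**Optional, for participants not yet enrolled.** Give the oral SDMT on an alternate form at Baseline Visit 2, keep the Visit 1 score for eligibility, and use the mean of the two as covariate; participants without the repeat keep their single score, with an indicator. Do this only if:
- a further alternate form is available;
- 5.2.7 is amended so that the Follow-Up Visit 1 SDMT alone is the primary outcome;
- the SAP states which baseline value LOCF carries forward.

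The cost is a short amendment, about 90 seconds of testing, and one more practice exposure before randomisation, expected to be the same in both arms.
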